#### **2.4.10 Further therapy after discontinuation of investigational medicinal product administration during the study**

A summary table, including the number of different regimen, will be provided for further anti-myeloma treatments based on WHO-DD coding.

Further anti-myeloma treatments will also be summarized by number of subsequent lines and drug class or agent, using selected drug classes or agents (e.g. daratumumab, elotuzumab, BCMA agents, PI, Immunomodulators [IMiD]).

#### **Time to next treatment**

TNT will be analyzed using Kaplan-Meier methods.

## 2.5 DATA HANDLING CONVENTIONS

### 2.5.1 General conventions

The following formulas will be used for computation of parameters.

#### *Renal function formulas*

Creatinine clearance will be estimated using the equation of MDRD:

$GFR \text{ (mL/min/1.73 m}^2\text{)} = 175 \times (\text{Scr} \times 0.0113)^{-1.154} \times (\text{Age})^{-0.203} \times (0.742 \text{ if Female}) \times (1.212 \text{ if African-American})$

with serum creatinine in  $\mu\text{mol/L}$  and age in years.

#### *Corrected calcium formula*

$\text{Corrected Calcium (mmol/L)} = (\text{Serum Calcium (in mmol/L)} + 0.8 \times 0.25 (4 - \text{serum albumin [in g/L]} \times 0.1))$

#### *Qol formulas*

*EORTC QLQ-C30 and QLQ-MY20 raw scores and scores calculation:*

For all scales, raw score (RS) = mean of the component items.

For functional scales,  $\text{Score} = (1 - ((\text{RS}-1)/\text{range})) \times 100$

For symptom scales/items and the global health status,  $\text{Score} = (\text{RS}-1)/\text{range} \times 100$

The range is the difference between the maximum and the minimum response to individual items.

See [Appendix F](#).

### 2.5.2 Data handling conventions for secondary efficacy variables

Not applicable.

### 2.5.3 Missing data

The analyses and summaries of continuous and categorical variables will be based on observed data only. Percentages will be calculated using as denominator the number of patients with non-missing observation in the considered population. When relevant, the number of patients with missing data is presented.

### ***Handling of disease characteristics missing/partial dates***

- If the day is missing, it will be estimated by 1.
- If the month is missing, it will be estimated by 1 (only for medical history variables).
- If the year is missing, no estimation will be performed.

### ***Handling of medication missing/partial dates***

No imputation of medication start/end dates or times will be performed. If a medication date or time is missing or partially missing and it cannot be determined whether it was taken prior or concomitantly, it will be considered a prior, concomitant, and post-treatment medication.

### ***Imputation of incomplete date for post anti-myeloma treatment start date***

For post anti-myeloma treatments, if the medication start date is missing, it will be imputed as follows:

- If the medication start day and month are missing and the medication start year is the same as treatment end year, the medication start date will be set equal to treatment end date + 1.
- If the medication start day and month are missing and the medication start year is after the treatment end year, the medication start day and month will each be set to 01.
- If the medication start day is missing and medication start year and month is the same as the treatment end year and month, the medication start day will be set equal to the treatment end day + 1.
- If the medication start day is missing and medication start month is before the treatment end month and the medication start year is the same as treatment end year, the medication start day will be set to 01.
- If the medication start day is missing and the medication start month is after the treatment end month and the medication start year is the same as treatment end year, the medication start day will be set to 01.
- If the medication start day is missing and the medication start month is not missing and the medication start year is after the treatment end year, the medication start day will be set to 01.
- If the medication start day, start month and start year is missing, the medication start date will be set equal to the treatment end date + 1.

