### **2.1.2 Prior or concomitant medications (other than anticancer therapies)**

All medications taken within 21 days before randomization and until the end of the study are to be reported in the case report form pages.

All medications will be coded using the World Health Organization-Drug Dictionary (WHO-DD) using the version MAR2018 or higher.

- Prior medications are those the patient used prior to first investigational medicinal product (IMP) intake. Prior medications can be discontinued before first administration or can be ongoing during treatment phase.
- Concomitant medications are any treatments received by the patient concomitantly to the IMP(s), from first administration to the last dose + 30 days. A given medication can be classified both as a prior medication and as a concomitant medication. Any anti-cancer treatment administered after the date of the last study treatment administration will not be considered as a concomitant medication and will be regarded as a further anti-myeloma therapy (see [Section 2.1.9](#)). The analysis of concomitant medications will include the IR medications (see below).
- Post treatment medications are those the patient took in the period running from 30 days after the last dose up to the end of the study.

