### **Determination of the PFS status for the primary analysis**

The following rules will be applied to determine if a patient has an event or is censored for the PFS primary analysis:

- For a patient who did not die and did not reach progressive disease before the cut-off date, the patient is censored and the censoring date is determined as follows:
  - If the patient received any further anti-myeloma treatment, then the censoring date is the date of last valid disease assessment without evidence of PD before the start of further anti-myeloma treatment, or the cut-off date, whichever comes first,
  - If the patient did not take any further anti-myeloma treatment then the censoring date is the date of last valid disease assessment without evidence of PD or the cut-off date, whichever comes first.
- For a patient who died or reached progressive disease before the cut-off date:
  - If the patient received any further anti-myeloma treatment before death or progression is documented, then the censoring date is the date of last valid disease assessment without evidence of PD before the start of further anti-myeloma treatment,
  - If the patient reached the PFS endpoint before initiation of further anti-myeloma treatment, the date of the event will be the date of progressive disease or death if no progression occurred.

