### ***Handling of missing/partial death dates***

- If the day of the death date is missing, it will be imputed as the first day of the month, except if the date of the patient's last contact is in the same month as the death date. In this case, the death date is imputed as the date of last contact + 1 day.
- If the day and month of the death date is missing, the date of death will be imputed to the first of January of the year, except if the date of the patient's last contact is in the same year as the death date. In this case, the death date will be imputed as the date of last contact + 1 day.
- If the death date is missing, no imputation will be done and the patient will be censored at the last contact date.

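### SAP 2.5.3 imputes partial start dates of further anti-myeloma therapy without checking the progression date, so a progression first dated after the last study dose can be censored in the primary PFS

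*SAP*

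**What the plan says.** SAP 2.5.3 has seven rules for an incomplete start date of further therapy.

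- Three use the day after treatment end. One covers a missing day in the same month and year ("the medication start day will be set equal to the treatment end day + 1"). One covers a missing day and month in the same year. One covers a wholly missing date ("If the medication start day, start month and start year is missing, the medication start date will be set equal to the treatment end date", plus one day).
- Three use the first of the known month. One of these applies when "the medication start month is after the treatment end month and the medication start year is the same as treatment end year".
- One uses 1 January: with day and month missing and a later year, "the medication start day and month will each be set to 01".

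No rule mentions the progression date, the last disease assessment or the end-of-treatment (EOT) visit. SAP 2.1.2 defines further therapy by its position after the last study dose: "Any anti-cancer treatment administered after the date of the last study treatment administration will not be considered as a concomitant medication".

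The date then decides PFS status. SAP 2.1.3.1 (Determination of the PFS status for the primary analysis) says: "If the patient received any further anti-myeloma treatment before death or progression is documented, then the censoring date is the date of last valid" assessment before that therapy. Appendix E, Table 13 gives the same outcome. SAP 2.1.3.1 lets an assessment made after further therapy confirm a PD, but this does not protect a first PD date that falls after the start.

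**The concern.** Progression is a common reason for starting further therapy, so PD often comes first and the therapy soon after. Setting the start as early as the known parts allow, given treatment end, can reverse that order. A true event in the primary PFS then becomes a censored observation, and the censoring is informative because it occurs just before a known progression.

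The date has wider use. TTP takes the PFS censoring rules (SAP 2.1.3.2.2), and the protocol summary says the same of DOR. Sensitivity analysis #4 uses the start date itself as the event date. PFS2 (SAP 2.1.3.2.3 and Appendix H) takes the first investigator PD after further therapy begins, so a start imputed too early can make the progression on study treatment count as the later one.

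**Working it through.** **Who is exposed.** I read treatment end as the date of the last study dose; SAP 2.5.3 does not define it. The problem needs an incomplete start date and a PD first dated after the imputed start. The main groups are:

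- patients who stop before PD and are followed monthly (Protocol 6.2.1);
- patients with PD first seen at the EOT visit, which Protocol 10.1.4 places 30 days after the last dose or before further therapy, whichever is first. Treatment end + 1 puts the therapy ahead of a visit designed to precede it;
- patients with imaging PD after the last dose, which needs no confirmation;
- patients stopped on investigator PD whose PD per the independent response committee (IRC) is dated later.

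**Rules applied to hypothetical dates.** In every row the true order is PD, then further therapy, so the correct status is event. The last column applies the bound proposed under the fix.

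| Missing part | Treatment end | PD | True start | Imputed start | Status now | Bounded start |
|---|---|---|---|---|---|---|
| Day, same month | 5 Mar 2018 | 20 Mar 2018 | 26 Mar 2018 | 6 Mar 2018 | censored | 21 Mar, event |
| Day, later month | 5 Mar 2018 | 10 Apr 2018 | 24 Apr 2018 | 1 Apr 2018 | censored | 11 Apr, event |
| Day, later year | 20 Nov 2017 | 12 Feb 2018 | 20 Feb 2018 | 1 Feb 2018 | censored | 13 Feb, event |
| Day and month, same year | 5 Mar 2018 | 2 Apr 2018 | 24 Apr 2018 | 6 Mar 2018 | censored | query |
| Day and month, later year | 20 Nov 2017 | 12 Feb 2018 | 1 Mar 2018 | 1 Jan 2018 | censored | query |
| Whole date | 5 Mar 2018 | 2 Apr 2018 | 24 Apr 2018 | 6 Mar 2018 | censored | query |
| Day, PD on treatment (control) | 5 Mar 2018 | 5 Feb 2018 | 20 Mar 2018 | 6 Mar 2018 | event | unchanged |

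Six rows flip and the control does not. The rule for a month before treatment end behaves the same way, but it concerns a start that SAP 2.1.2 would not normally class as further therapy. In sensitivity analysis #4 the first row would be dated 6 March instead of 20 March (14 days early), and the second 1 April instead of 10 April (9 days early).

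**How often the order flips, given the pattern.** Take a 30-day month with equal weight on every date combination.

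- Treatment end < PD < start, all in one month: C(30,3) = 4060 combinations. PD falls exactly on treatment end + 1 in 28 × 29 / 2 = 406 (ties). The other 3654 (90%) flip.
- PD < start, both in one later month: C(30,2) = 435. PD falls on the first in 29 (ties). The other 406 (93%) flip.

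These are conditional shares, not estimates of how many patients are affected. Ties are unresolved: Table 13 counts an event only if PD is prior to further therapy, and censors only if therapy starts before PD. A tie meets neither condition.

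**Scale.** The plan's event count is reproduced: 4 × (1.960 + 1.282)² / (ln 0.60)² = 161.1, rounded up to 162. Power is Φ(√d / 2 × |ln 0.60| − 1.960). At d = 162 this is 90.2%. The number of lost events is not in the documents. Under assumed losses that are not replaced, power is 89.6% (3 lost), 89.3% (5), 88.3% (10) and 87.0% (16). The cut-off waits for 162 events, so lost events would mainly delay it.

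**The case against.** **Ordinary on-treatment progression.** A reader might infer that typical progressions are lost, for example a last dose on Day 22, first PD on the Day 29 sample and no further dose. The documents do not support this for laboratory PD. Protocol 8.2 keeps the patient on treatment until PD is confirmed, and the SAP dates PD at the first indicating assessment. PD then usually precedes treatment end and the event is kept, as in the control row. This objection stands and narrows the exposed group.

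**Contrast with death dates.** For deaths in the month of last contact, the SAP says "In this case, the death date is imputed as the date of last contact + 1 day". A reader might infer that only deaths are bounded by a known date. That is not so: three of the seven rules here are bounded by treatment end, and both sets of rules otherwise fall back to the first of the month or 1 January.

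**Existing safeguards.** Sensitivity analysis #1 ignores further therapy and so recovers every PFS event lost this way. SAP 2.4.4.1 tabulates, by arm, events seen after censoring. Both stand, but neither isolates the imputation. Analysis #1 also adds PDs that truly followed further therapy, and the table mixes imputed with complete dates.

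**Direction of bias.** A reader might infer a bias against one arm, or a fixed loss such as 2% to 5% of the 162 events (3 to 8). Neither follows from the documents. If more control patients progress and move on, the loss could fall more on control, which would be conservative for superiority; that too is only conjecture.

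**Bias of the remedy.** A PD bound makes the imputed date depend on the outcome. For year-only or wholly missing dates this is a serious objection, because the protocol expects some patients to start further therapy without PD. It stands, and the bound should not be the main rule there.

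**Conclusion.** The point holds in limited form. As written, the SAP can place further therapy before a progression that came first and so censor a true primary event. This applies to patients with an incomplete start date whose first PD is dated after the last study dose. The mechanism follows from the text. The size does not: it depends on how many start dates are incomplete, which the documents do not report. The plausible effect on power is small, since the cut-off is event-driven. The real issue is informative censoring of unknown extent, plus misdated or misattributed events in sensitivity analysis #4 and PFS2. It is worth correcting because the correction is cheap and SAP 2.5.3 still governs PFS2 at the later OS analyses.

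**What to change.** 1. In SAP 2.5.3, when only the start day is missing and the documented PD falls in the same month and year, impute the start as the later of the current rule's date and PD + 1 day, capped at the end of that month. State that a start on the PD date counts as after PD; this also covers a PD on the last day of a month. Name the PD used: IRC for IRC endpoints, investigator for PFS2.
2. Query year-only and wholly missing dates. If unresolved, keep the current rule and show the PD-bounded alternative as a sensitivity analysis.
3. Report by arm the number of imputed starts and the number of PFS and PFS2 outcomes that depend on them.
4. SAP Table 1 shows that the primary analysis preceded version 3, and Table 10 plans no later PFS analysis. Apply the bound prospectively to PFS2, and present the bounded primary PFS as a supplementary rerun beside the reported one, not in its place.

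The cost is a short addition to the SAP, minor programming and some date queries; no new assessments are needed. The downside is that therapy truly started earlier than PD in the same month would be counted as starting after it, which is why both versions should be shown.

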### ***Handling of missing/partial death dates***

- If the day of the death date is missing, it will be imputed as the first day of the month, except if the date of the patient's last contact is in the same month as the death date. In this case, the death date is imputed as the date of last contact + 1 day.
- If the day and month of the death date is missing, the date of death will be imputed to the first of January of the year, except if the date of the patient's last contact is in the same year as the death date. In this case, the death date will be imputed as the date of last contact + 1 day.
- If the death date is missing, no imputation will be done and the patient will be censored at the last contact date.

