11.4.2.2 Analyses of secondary efficacy endpoints

11.4.2.2.1 Analysis of key secondary efficacy endpoints

The key secondary efficacy endpoints are ORR and OS.

Best overall response, ORR and clinical benefit rate will be summarized using the ITT population with descriptive statistics at the time of the primary analysis on PFS (based on data collected up to the PFS analysis cut-off date). Confidence intervals will be computed using the Clopper-Pearson method. ORR will be compared between treatment groups using Cochran Mantel Haenszel stratified method.

The analysis on key secondary endpoint will also consist of OS comparison between the IPd group versus the Pd group through a 1-sided log-rank test procedure. Patients without death prior to the analysis cut-off date will be censored at the last date the patient was known to be alive or the cut-off date, whichever is earlier. This analysis will be performed on the ITT population at the time of the primary analysis on PFS (at about 36% information fraction), at the time when approximately 90% of OS events have occurred, and at the end of the study (final analysis on OS). An O'Brien and Fleming α -spending function will be used to obtain the nominal significance levels for the interim and final analyses of survival. The nominal significance (one-sided) level for the final survival comparisons would be of 0.0200 for 220 death events (corresponding to a HR of 0.758).

If death is not observed before the analysis data cut-off date, data on OS will be censored at the date patient is known to be alive or at the cut-off date, whichever comes first.

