#### **Overall survival (OS)**

OS is defined as the time from the date of randomization to date of death from any cause. If death is not observed before the analysis data cut-off date, OS will be censored at the last date that the patient is known to be alive or at the cut-off date, whichever comes first.

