## **OS**

The analysis of OS will consist of comparison between IPd group versus Pd group through a 1-sided log-rank test procedure stratified by stratification factors as entered in the IRT (ie, age and number of previous lines of therapy).

This analysis will be performed at the time of the primary analysis on PFS (at about 36% information fraction), at the second interim analysis on OS and at the end of the study (final analysis on OS). An O'Brien and Fleming  $\alpha$  spending function will be used to obtain the nominal significance levels for the interim and final analyses of survival. The nominal significance (one-sided) level for the final survival comparisons would be of 0.0200 for 220 death events (corresponding to a HR of 0.758).

In addition, the following estimates will be provided for OS:

- The hazard ratio (HR) and its 95% CI will be estimated using the Cox proportional hazards model stratified by the same stratifications factors as those used for the log-rank test. Underlying assumptions of the Cox proportional hazard model will be assessed by graphical methods (ie, log-log graphical methods).
- OS data will be analyzed using the Kaplan-Meier method by treatment group in the ITT population:
  - Kaplan-Meier estimates of the 25th, 50th and 75th percentiles and their associated 95% CIs will be provided,
  - Number of patients at risk as well as the probabilities of surviving at least 6, 12, 18, 24 and 36 months with 95% CI will be estimated for each treatment group using the Kaplan-Meier method.
- The number of censored patients, the reasons for their censoring (ie, alive at the cut-off date, alive at the last contact before the cut-off date, and lost to follow-up) and the time between the date of last contact and the cut-off date will be summarized by treatment group.
- Kaplan-Meier curves will be plotted.

Sensitivity analyses adjusting OS for switch to subsequent anti-cancer treatment could also be performed at interim and/or final analyses (e.g. using inverse probability of censoring weighting (IPCW) method) (7).

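### SAP 2.5.3 censors in OS, as a survivor, a patient known to have died whose death date is wholly missing

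*SAP*

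**What the plan says.** SAP 2.5.3, under Handling of missing/partial death dates, has three rules.

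- **Day missing.** "If the day of the death date is missing, it will be imputed as the first day of the month". If the last contact falls in that month, the day after last contact is used instead.
- **Day and month missing.** The date becomes 1 January of the year, unless the last contact is in the same year: "In this case, the death date will be imputed as the date of last contact + 1 day".
- **Whole date missing.** "If the death date is missing, no imputation will be done and the patient will be censored at the last contact date".

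The endpoint text is in SAP 2.1.3.2.1: "OS is defined as the time from the date of randomization to date of death from any cause". The same section limits censoring: "If death is not observed before the analysis data cut-off date, OS will be censored at the last date". The date meant is the latest one on which survival was confirmed, capped by the cut-off. Protocol 11.4.2.2.1 agrees: "Patients without death prior to the analysis cut-off date will be censored at the last date the patient was known to be alive". It applies the same cap.

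SAP 2.4.4.2 lists the OS censoring reasons to be reported: "alive at the cut-off date, alive at the last contact before the cut-off date, and lost to follow-up".

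For another wholly missing date, the start of further anti-myeloma therapy, SAP 2.5.3 does impute: "If the medication start day, start month and start year is missing, the medication start date will be set equal to the treatment end date" plus one day.

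**The concern.** The first two rules keep the death as an event and accept an approximate date. The third drops the event because the date is unknown, although the fact of death is known. A patient reported dead before the cut-off does not belong to the group for which either document defines OS censoring. No other section restores such a death as an event or provides a sensitivity analysis for it.

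Censoring that happens because the patient died is informative. It lowers the estimated hazard in the arm where it occurs. OS is a key secondary endpoint, formally tested after PFS and ORR, so a shift in its hazard ratio matters if the cases fall unevenly between arms. The trial is open-label, and survival after progression is collected through 3-monthly contacts that may in exceptional cases be a telephone call to a caregiver or relative (Protocol 1.2, follow-up footnote). That is a plausible route to a reported death without a date.

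**Working it through.** **1. The rule applied to one patient.** Take a last contact on 10 March, and suppose the patient is later recorded as dead.

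| Recorded for the death | Result under SAP 2.5.3 |
|---|---|
| Same year, no day or month | Event on 11 March |
| Nothing | Censored on 10 March |

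What is known about survival is nearly the same in both rows. Event status depends on whether the year was filled in.

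**2. Reproducing the plan's OS design.** Inputs from Protocol 11.1, SAP 1.3 and SAP 3: HR 0.685, 220 deaths, 1:1 allocation, one-sided 0.025, interim looks at about 80 and 198 deaths.

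Power = Φ(|ln HR|·√d/2 − z). With |ln 0.685| = 0.3783 and √220 = 14.832, the first term is 2.806. Subtracting 1.960 gives 0.846 and power 80.1%. The SAP states 80%.

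With three looks and O'Brien-Fleming-type spending, power is 79.2%; the protocol states 79.3%. The second and final one-sided levels come out at 0.0181 and 0.0200, as stated.

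**3. Loss of events.** The number of undated deaths is not in the documents, so it is varied. Same formula, single look at 0.0200 (z = 2.054), true HR held at 0.685, 220 known deaths:

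| Undated deaths | Events analysed | Power |
|---|---|---|
| 0 | 220 | 77.4% |
| 1 | 219 | 77.2% |
| 5 | 215 | 76.4% |
| 11 | 209 | 75.2% |

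Five cases cost about one percentage point.

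**4. Shift in the hazard ratio.** This was simulated with 2,000 runs per case: exponential OS with a control median of 13 months and HR 0.685, 300 patients, and cut-off at the 220th death. Two settings are assumptions: uniform accrual over 18 months, and a last contact 0 to 3 months before death. Undated deaths are drawn at random from the deaths in the arm concerned.

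| Undated deaths | HR, all deaths counted | HR, SAP rule | HR, event at last contact + 1 day |
|---|---|---|---|
| 5 in each arm | 0.684 | 0.678 | 0.684 |
| 5 in IPd only | 0.683 | 0.650 | 0.685 |
| 5 in Pd only | 0.686 | 0.714 | 0.684 |

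The second column varies between rows through simulation error. Within rows, the one-sided cases shift the HR by about 0.03, in favour of IPd or against it depending on the arm.

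A rough check, assuming the deaths split evenly at 110 per arm: 5/110 = 4.5%. Then 0.683 × 105/110 = 0.652 and 0.686 × 110/105 = 0.719, close to the simulated 0.650 and 0.714.

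**The case against.** **It should be rare, and may never occur.** After progression, patients are contacted every 3 months (Protocol 6.2.1). A missed survival contact is to be retrieved at once (Protocol 1.2, follow-up footnote). For patients who stop attending, sites search family, physicians and registries for vital status (Protocol 10.3.4). Where two contacts in one year bracket the death, the year can be deduced and the partial-date rule then applies. This stands as a point about frequency. It does not alter what the rule does to a death that remains undated.

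**The death is not hidden.** SAP 2.4.5.2 tabulates deaths by treatment received. The OS censoring reason for patients alive at last contact could also be said to describe status on the censoring date. This stands in part: the death can be seen in the safety tables, but the OS estimate still treats the patient as a survivor, and the censoring summary would not show otherwise.

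**Censoring can be right.** If the death came after the cut-off, the patient should be censored. That is correct, but the rule does not separate this case from a death reported before the cut-off.

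**The replacement is not neutral.** The day after the patient was last known alive is the earliest possible death date. In the SAP's partial-date rules it is the exception, not the default. Both statements are true, which is why a second analysis at a later date is needed.

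**Conclusion.** The point holds for OS and is minor. SAP 2.5.3 contradicts the OS censoring definition in both documents for a known death with no date, and it makes the censoring informative. The effect is negligible if cases are balanced between arms, and about 0.03 on the HR if 5 fall in one arm. That second figure rests on an assumed count, a one-sided allocation for which the documents give no reason, and the simulation settings above.

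A reader might infer three stronger things that the documents do not support.

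- **That these deaths are also left out of the 220-death trigger.** Neither document says how the trigger is counted. If only dated deaths count, the cut-off comes later and final power is kept; the losses in step 3 arise only if undated deaths do count towards the trigger.
- **That the primary PFS analysis is affected to a similar degree.** The rule censors at last contact, whereas PFS is censored at the last valid disease assessment (SAP 2.1.3.1), so it reads as an OS rule, although it is not expressly limited to OS. Patients without progression are followed monthly, and those out of contact after progression would normally already have a PFS event. Any PFS effect is marginal.
- **That wholly undated deaths are known to have occurred.** SAP 1.6, Table 1 says the convention was added in version 2 for cases reported in the database, but it does not separate missing from partial dates.

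**What to change.** Replace the third rule in SAP 2.5.3 with:

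> If the death date is completely missing and the death was reported on or before the cut-off date, the patient is counted as an OS event, with the date imputed as the last date known alive + 1 day. A sensitivity analysis uses the date the death was reported, and the number of such cases is given by arm.

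This extends the one-day convention that the SAP already uses for partial dates. The last date known alive is clearer than last contact, because a call in which a relative reports the death might itself be recorded as a contact. An undated death first reported after the cut-off cannot be placed on either side of it and would still be censored.

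The cost is one sentence and one extra OS run. The main imputation uses the earliest possible date; together with the report date it brackets the true date of each death. The current rule dates from SAP version 2 (November 2018), and SAP version 3 was issued after the primary analysis, when the first OS interim was planned. Changing what counts as an OS event at this stage of an open-label trial should therefore be recorded with its date and reason. If there are no such cases, no result changes.
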